3.3. Study Endpoints

(a) Primary Endpoint

Clinical pregnancy, defined as presence of one or more intrauterine gestational sacs after 6 weeks estimated gestational age.

(b) Secondary Endpoint

- 1) Ongoing pregnancy, defined as presence of fetal heartbeat after 12 weeks of gestation.
- 2) Live birth, defined as baby survival after 20 weeks of gestation.
- 3) Abortion and miscarriage rates.
- 4) Frequency and intensity of adverse events (AEs).

CLINICAL STUDY PROTOCOL

Title: Multi-national, multi-center randomized controlled trial to evaluate the clinical utility of non-invasive endometrial receptivity test (ora™) in patients with implantation failure

Doc. No.	ORA-PTL-2024-01
Version	1.0
Date	2024/01/10

4. Study Population

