4.3. Exclusion Criteria

- (a) Known uterine factor (such as endometriosis, uterine fibroids) impacting the endometrium.
- (b) Presence of any clinically relevant systemic disease (such as immune disease) that contraindicates assisted reproductive technology.
- (c) Body mass index (BMI) exceeds than 30 kg/m².

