5.6. Research Process

(a) Randomization:

After signing the ICF, the investigator will assign a **subject code** to each enrolled subject. This subject code will consist of two parts: the center identification number and the subject identification number. For instance, TW01-001.

- 1) The center identification number is structured using the first two letters of the country name followed by a two-digit site number. Examples include TW01, TW02, SG01, JP01, etc.
- 2) Within each age category at each center, subjects will receive a subject identification number assigned based on their order of inclusion in the study. The first subject enrolled will be labeled as 001, followed by 002, and so forth, maintaining chronological order.

Once the subject receives the unique subject code, the subject will be randomized to one of the two study groups through a simple 1: 1 randomization program stratified by center (to avoid bias). The randomization number will be assigned to each subject included in the study, as well as their corresponding group. The randomization program will be set up by the Inti Inc., Taiwan.

For example, the randomization process for a subject attending the initial clinical site in Taiwan:

Subject code	Randomization number	Group
TW01-001	1	Control
TW01-002	2	Study
TW01-003	3	Study
TW01-004	4	Control
TW01-005	5	Control
TW01-006	6	Study

CLINICAL STUDY PROTOCOL

Title: Multi-national, multi-center randomized controlled trial to evaluate the clinical utility of non-invasive endometrial receptivity test (ora™) in patients with implantation failure

Doc. No.	ORA-PTL-2024-01
Version	1.0
Date	2024/01/10

- (b) Subjects will undergo the hormone replacement therapy (HRT) in a frozen embryo transfer (FET) cycle. The HRT treatment cycle will be performed following medical criteria and in accordance with the usual practice of the clinic and the doctors. Ideally, the subjects in the control and study groups should follow identical drug prescription program.
- (c) Endometrial receptivity test by ora™:
- 1) Study group subjects will undergo blood sampling for the ora™ test on the fifth day of progesterone administration in a **mock cycle** (120 ± 3 hours after the first progesterone injection); the control group subjects will undergo blood sampling for the ora™ test and frozen embryo transfer at the standard time (120 ± 3 hours after the first progesterone injection) for data collection.

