- 3) Around 12 weeks after estimated gestational age, an ultrasound will be performed to assess the presence of a fetal heartbeat, providing an estimate of ongoing pregnancy.
- 4) Around 20 weeks after estimated gestational age, live birth will be evaluated.
- 5) Abortion and miscarriage rates would be calculated.

[figure not shown]

Fig. 1 Flowchart of the clinical trial

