7.1. Sample size calculation

The sample size calculation for the two-armed endpoint suggests that obtaining data from 650 participants (325 subjects for each group). This sample size is adequate to detect a 10% difference in clinical pregnancy outcomes between groups given an alpha level of $p < 0.05$ and a power of 0.8 and using 50% anticipated LB in the control arm (based on current success rates among euploid embryo transfers conducted with standard timing protocol). Accounting for 10-20% dropout rate, the goal is to enroll 800 subjects in total.

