7.2. Data Evaluation and Statistical Considerations

- (a) The outcome of clinical pregnancy and live birth rate, etc. per transfer will be compared between the study and control groups by chi-square analysis.
- (b) The quantitative outcomes such as gestational age and BMI, etc. will be compared between treatment groups by the Mann-Whitney U test.

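### Section 7.2(b) and the synopsis test BMI and gestational age between arms as outcomes, but BMI is in effect a baseline variable and gestational age exists only in women who conceive (minor)

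*Protocol*

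**What the plan says.** Protocol section 7.2(b), and item 2 of the statistical methodology in the synopsis, state: "The quantitative outcomes such as gestational age and BMI, etc. will be compared between treatment groups by the Mann-Whitney U test".

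The rest of the protocol treats these two variables as follows.

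- **BMI.** Outside that sentence, BMI appears as an outcome-related variable nowhere. It is an exclusion criterion in section 4.3 and the synopsis: "Body mass index (BMI) exceeds than 30 kg/m²". No later BMI measurement is described.
- **Gestational age.** It is not among the endpoints in section 3.3. The primary endpoint there is yes or no: "Clinical pregnancy, defined as presence of one or more intrauterine gestational sacs after 6 weeks estimated gestational age". The follow-up in section 5.6(e) is timed by gestational week, for example "Around 12 weeks after estimated gestational age, an ultrasound will be performed to assess the presence of a fetal heartbeat", and the last assessment is at about 20 weeks.

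Allocation (section 5.6(a)) is by a "simple 1: 1 randomization program stratified by center". The planning scenario in section 7.1 is to "detect a 10% difference in clinical pregnancy outcomes between groups", with 325 per group, "using 50% anticipated LB in the control arm".

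**The concern.** An outcome test between randomised arms should tell the reader something about the treatment. Neither variable fits that purpose well, for different reasons.

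BMI is used to decide eligibility, so under randomisation any difference between arms is chance. A small p-value would carry no information about ora, but could raise needless doubt about the allocation.

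Gestational age is undefined for a woman who does not conceive. A Mann-Whitney comparison of it is therefore a comparison of pregnant women only. If ora works as hoped, the pregnant women in the study arm are those who would have conceived anyway plus some who would not. If those additional pregnancies tend to end earlier, the study arm shows shorter gestation even though no pregnancy was cut short by the timing change. A reader could take that p-value as a signal against the test.

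**Working it through.** **Plan's own figure.** The protocol gives no figure for this analysis. The 325 per group in section 7.1 serves here only as the trial size. For 50% v 60% at power 0.80, n = [z_α√(2p̄q̄) + z_β√(p₁q₁ + p₂q₂)]²/d² with one-sided α = 0.05 gives [1.645√0.495 + 0.842√0.49]²/0.01 ≈ 305. The continuity correction raises it to 325, an exact match. (A two-sided calculation without correction gives 388; that is a separate matter.)

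**BMI.** Both arms are random samples from one population, so the rejection rate equals α. A simulation with 325 per arm gave 5.2%.

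**Who contributes a gestational age.** Taking 50% v 60% as the pregnancy rates:

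- Control: 325 × 0.50 = 162.5 women. Study: 325 × 0.60 = 195 women.
- Without a value: 650 − 357.5 = 292.5, or 45%.
- Study-arm pregnancies that exist only because of ora: 195 − 162.5 = 32.5, and 32.5/195 = 1 in 6.

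**How selection enters.** Assume 12% of the pregnancies that would occur under either strategy are lost, and a fraction L of the added ones. Loss among pregnant women in the study arm is (162.5 × 0.12 + 32.5 × L)/195. Pregnancies that last, per woman, are (162.5 × 0.88 + 32.5 × (1 − L))/325 in the study arm and 162.5 × 0.88/325 = 44.0% in control.

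| L (assumed) | Loss among pregnant, control | Loss among pregnant, study | Lasting pregnancy per woman, control | Lasting pregnancy per woman, study |
|---|---|---|---|---|
| 12% | 12% | 12.0% | 44.0% | 52.8% |
| 30% | 12% | 15.0% | 44.0% | 51.0% |
| 50% | 12% | 18.3% | 44.0% | 49.0% |
| 70% | 12% | 21.7% | 44.0% | 47.0% |

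The pregnant-only view looks worse for ora as L rises. The per-woman view favours ora in every row, as it must when no existing pregnancy is shortened.

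**Effect on the test.** Simulation, 2,500 to 3,000 trials per scenario: 325 per arm, 50% v 60% pregnant, birth at 38.8 weeks (SD 1.8) unless lost, follow-up to birth, two-sided Mann-Whitney at 0.05 in pregnant women only. Share of trials declaring shorter gestation in the study arm, over repeated runs:

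| L | Declared shorter with ora |
|---|---|
| 12% | 2–3% |
| 30% | 6–7% |
| 50% | 17–19% |
| 70% | 35–36% |

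The nominal rate in that direction is 2.5%. If ora adds no pregnancies, the test rejects in 5.4% of trials, two-sided, which is its level.

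**Sensitivity.** The size depends on what is assumed. If gestational age is capped at the last scheduled assessment, about 20 weeks, the rates become about 2–3%, 12–13%, 38% and 67%. If the added pregnancies are not lost more often but simply end 1 to 6 weeks earlier (mean 38.5 weeks, SD 2 in the others), the range is 11% to 76%. None of these loss rates or durations is in the protocol.

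**The case against.** The strongest reply is that this matters little. Neither variable is a listed endpoint, and the primary chi-square test on clinical pregnancy is untouched. Ongoing pregnancy and live birth are compared per transfer, so a woman who has a transfer and does not conceive already counts as a failure; those results would stand beside any gestational-age p-value. The sentence may be only a loose general rule for continuous variables. A BMI test biases no treatment estimate, and that BMI is measured only before randomisation is inferred from its use as an exclusion criterion, since no measurement time is given. All of this stands, and it sets the severity at minor.

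A false signal on gestational age also needs two things at once: ora must add pregnancies, and the added ones must be shorter or more fragile. The protocol plans for the first but says nothing to suggest the second. At equal loss the false-signal rate is nominal, and the high rates need the added pregnancies to be lost at 50% to 70% against 12% in the others. That stands too.

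The time point and analysis set for gestational age are commonly left to the SAP, which is not shown, so their absence is not counted here. The reply does not remove the stated rule itself: the protocol calls both variables outcomes and commits to a between-arm test of each. No choice of time point or analysis set gives a gestational age to a woman who did not conceive.

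**Conclusion.** The point holds at minor severity. As stated, the BMI test can detect only chance imbalance. The gestational-age test compares groups formed after randomisation by the event that ora is meant to change.

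A reader might infer that the gestational-age p-value says nothing about ora, or that the test is invalid outright. The documents do not support that. It is a valid test of no difference if ora does not change who conceives, and it keeps its level if the added pregnancies do not differ in duration. Otherwise it mixes any true effect with selection. A reader might also infer that a false harm signal is to be expected. It is only possible: the illustrative rates, from 2–3% up to 35–36% against a nominal 2.5%, rest on assumed loss rates and on the planned 50% v 60%. The primary analysis is unaffected.

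**What to change.** Change section 7.2(b) and item 2 of the synopsis methodology in three ways.

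1. Remove BMI from the outcomes. Summarise it by arm with the other baseline characteristics, without a significance test.
2. Report gestational age among pregnant women descriptively by arm, without a between-arm p-value.
3. Base inference on whether pregnancies last on the ongoing pregnancy and live birth endpoints already in section 3.3, with women who do not conceive counted as not having the event.

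No new endpoint, composite score or covariate adjustment is needed: the listed endpoints already carry the information. The cost is wording in two places, carried into the SAP, with no new data or visits. The downside is the loss of one p-value on a variable that is not an endpoint.

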7.3. Data Management

- (a) Data management organization and procedures
 - 1) Data collection and accurate documentation are the responsibility of the study staff under the supervision of the investigator. All source documents must be reviewed by study personnel and data entry staff, which will ensure that they are accurate and complete.
 - 2) CRFs are provided for each subject in printed or electronic format. Source documentation must be available for the following to confirm data collected in the CRF. The sponsor will review CRFs for accuracy and completeness; any discrepancies will be resolved with the investigator or designee, as appropriate.
- (b) Electronic data validation, verification, and protection procedures

After upload of the data into the study database they will be verified for accuracy and consistency with the data sources

CLINICAL STUDY PROTOCOL

Title: Multi-national, multi-center randomized controlled trial to evaluate the clinical utility of non-invasive endometrial receptivity test (ora™) in patients with implantation failure

Doc. No.	ORA-PTL-2024-01
Version	1.0
Date	2024/01/10

8. Adverse events (AE), Adverse reactions and medical device deficiency

During and following a subject's participation in the study, the investigator/institution should ensure that adequate medical care is provided to a subject for any adverse events, including clinically significant laboratory values, related to the trial. The investigator/institution should inform a subject when medical care is needed for intercurrent illness(es) of which the investigator becomes aware.

In the event medical care to a subject is required, the medical care given to, and medical decisions made on behalf of, subjects should always be the responsibility of a qualified physician or, when appropriate, other healthcare providers.

8.1. Adverse Events

An Adverse Event (AE) is defined as any untoward medical occurrence, unintended disease or injury in subjects, users or other persons, that is considered a change from baseline or pre-study status, whether or not related to the investigational medical device.

Any pre-existing medical condition or symptoms present in a subject will not be considered an Adverse Event in this study, unless it worsens because of this study.

All Adverse Events (AEs) will be reported on an AE Case Report Form and will include the following: Date/time of onset, description of the event, the duration of the event, the severity of the event, assessment of the relation of the event to the study device and procedure, description of action taken (if any) and the event outcome.

8.2. Serious Adverse Events

A Serious Adverse Event (SAE) is defined as an adverse event that is anticipated or unanticipated and which reasonably suggests that one of the manufacturers' devices has or may have caused or contributed to a death or serious injury.

A Serious Adverse Event is an Adverse Event that led to: (a) death, (b) serious deterioration in the health of the subject that either resulted in a (i) life-threatening illness or injury or (ii) permanent impairment of a body structure or a body function, or (iii) in-patient or prolonged hospitalization or (iv) medical or surgical intervention to prevent life-threatening illness or injury or permanent impairment to a body structure or a body function or (c) fetal distress, fetal death or a congenital abnormality or birth defect.

These events are typically reportable to health authorities. Serious Adverse Events will be reported to the Sponsor within 24 hours of knowledge of the event.

	CLINICAL STUDY PROTOCOL		
	Doc. No.	ORA-PTL-2024-01	
	Version	1.0	
Title: Multi-national, multi-center randomized controlled trial to evaluate the clinical utility of non-invasive endometrial receptivity test (ora™) in patients with implantation failure		Date	2024/01/10

9. Regulatory, Ethical and Study Oversight Considerations

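### Section 8.2 defines a serious adverse event in two ways ahead of one 24-hour reporting rule, and section 8.1 lets attribution decide whether worsening of a pre-existing condition counts as an adverse event

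*Protocol*

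**What the plan says.** Section 8.2 has two consecutive definitions.

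- Paragraph 1 defines an SAE as an adverse event reasonably suggesting that one of the manufacturer's devices "has or may have caused or contributed to a death or serious injury".
- Paragraph 2 reads: "A Serious Adverse Event is an Adverse Event that led to: (a) death, (b) serious deterioration in the health of the subject". The serious deterioration in item (b) includes "in-patient or prolonged hospitalization". Item (c) adds fetal distress or death and congenital defects. No causality condition appears.

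The reporting rule comes after both and uses the bare term: "Serious Adverse Events will be reported to the Sponsor within 24 hours of knowledge of the event".

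Section 8.1 defines an adverse event as an untoward occurrence in subjects, users or anyone else that is a change from baseline, "whether or not related to the investigational medical device". A pre-existing condition, however, "will not be considered an Adverse Event in this study, unless it worsens because of this study". On recording, the section says: "All Adverse Events (AEs) will be reported on an AE Case Report Form". One item on that form is "assessment of the relation of the event to the study device and procedure".

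Section 3.3 makes the frequency and intensity of AEs a secondary endpoint. Section 9.1 has the investigator notify the IRB/IEC of SAEs and other important safety findings, without saying which SAE definition is meant.

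**The concern.** A site handling a serious event needs one test for whether the 24-hour clock starts. Section 8.2 offers two, and they give different answers for foreseeable events. The trial aims at pregnancy and counts pregnancy loss as a secondary endpoint, so fetal events will arise; they are named only in paragraph 2. The trial is multi-national (the example site codes in section 5.6 cover three countries), so sites may settle the question differently.

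The 8.1 exception is a separate fault with a different consequence. It uses attribution to decide whether an event is recorded at all, although the form already has a place to record attribution. Women with pre-existing conditions can enter: section 4.3 excludes systemic disease only where it rules out assisted reproduction.

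Both attribution conditions operate in an unblinded trial. Both arms give blood for the test, but only the study group has a mock cycle and a transfer time set by the result. Attribution could therefore differ by arm, through paragraph 1 of 8.2 or through the 8.1 exception.

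**Working it through.** The protocol gives no AE or SAE rate, so there is no figure to reproduce and no event count to calculate. The check is to apply the wording of 8.1 and 8.2 to each type of event.

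**Step 1: what each paragraph requires.** Both start from an adverse event. Paragraph 1 then needs suspected device causation of death or serious injury (the latter undefined). Paragraph 2 needs a listed outcome; its item (b) is confined to the subject's own health.

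**Step 2: apply 8.1, then each paragraph.**

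| Event | AE under 8.1 | SAE by paragraph 1 | SAE by paragraph 2 |
|---|---|---|---|
| A. Subject; listed outcome that is also a death or serious injury; device suspected | Yes | Yes | Yes |
| B. Subject; listed outcome; judged unrelated to the device; not a pre-existing condition | Yes | No | Yes |
| C. Fetal event listed in item (c); judged unrelated to the device | Yes | No | Yes |
| D. Non-fatal serious injury to a user or other person; device suspected | Yes | Yes | Not under item (b) |
| E. Subject; pre-existing condition worsens to in-patient admission; judged unrelated to the study | No | No | No |

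Rows B and C meet only paragraph 2. Row D can meet only paragraph 1. Neither definition is a subset of the other.

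**Step 3: is the 24-hour report due?** Section 8.2 permits four readings.

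| Event | Either suffices | Both required | Paragraph 1 governs | Paragraph 2 governs |
|---|---|---|---|---|
| A | Yes | Yes | Yes | Yes |
| B | Yes | No | No | Yes |
| C | Yes | No | No | Yes |
| D | Yes | No | Yes | No |
| E | No | No | No | No |

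Reporting of three of the five types (B, C, D) depends on the reading. One (A) is always reported and one (E) never is.

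**Step 4: what is lost.** B, C and D are adverse events under 8.1 and so belong on the AE form; at risk are SAE classification and speed. E fails the 8.1 exception, so it is not on the form, its relatedness is not recorded, and it is not counted in the AE secondary endpoint.

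**Step 5: does one edit cure both faults?** No. Since both paragraphs of 8.2 start from an adverse event, reconciling them settles B, C and D but leaves E out. Only a change to 8.1 brings E in.

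**Step 6: is either point resolved elsewhere?** No. Section 9.1 requires adherence to ISO 14155:2020 but does not say that its definitions replace the wording of 8.2.

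**The case against.** The strongest reply is that nothing in 8.2 requires an event to satisfy both paragraphs. Read as alternatives, they send B, C and D to the sponsor within 24 hours. Paragraph 2 is also the more detailed and stands directly above the reporting rule, so many sites would apply it. That is fair, and divergence between sites is a risk rather than an established fact. But the text does not state the generous reading. Paragraph 1 is worded as the definition, and if paragraph 2 merely explains what serious means there, causality governs and B and C drop out.

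On 8.1, it can be said that the exception refers to the study as a whole, which is wider than the device, so it is a narrow carve-out and not a strict contradiction. A new complication of an old condition might also be read as a fresh change from baseline. Both points soften the conflict. On its plain reading, though, worsening judged unrelated to the study is still excluded by one sentence after being included by another.

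Three stronger inferences should be resisted.

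- A reader might infer that unrelated serious events go unrecorded. Apart from worsening of a pre-existing condition, they reach the AE form; the sponsor reviews CRFs (section 7.3) and monitors verify source data (section 9.5). IRB/IEC notification is also less exposed, because section 9.1 reaches beyond SAEs.
- A reader might infer that safety reporting will be biased between arms. The documents support only the possibility.
- A reader might treat paragraph 1 as simply the device-related part of paragraph 2. Row D shows that it is not.

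**Conclusion.** The concern stands as an internal inconsistency in the safety definitions that should be corrected. Section 8.2 leaves the 24-hour report for unrelated serious events, fetal events and suspected device injuries to non-subjects dependent on an unstated choice between two definitions. Section 8.1, on its plain reading, removes unrelated worsening of pre-existing conditions from the AE form, the AE secondary endpoint and SAE status.

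In scope, two definitions precede one rule covering all enrolled subjects, up to 800. That is a measure of reach, not of harm: the number of affected events cannot be derived. The primary endpoint and the sample size are unaffected.

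Confidence is high that there are two unranked definitions and that the 8.1 exception turns on attribution. The conclusion on row E rests on reading the exception literally. Differences between sites or arms remain possibilities.

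**What to change.** 1. In 8.2, write one causality-neutral, outcome-based SAE definition. Let it cover everyone the AE definition covers (subjects, users and other persons), keep the fetal outcomes, apply it identically in both arms, and name it as the trigger for the 24-hour sponsor report.
2. Keep paragraph 1 as a separate, labelled device-related category, identified from the relatedness item already on the AE form. Do not word it as a subset of the merged definition unless that definition has been widened as in item 1; otherwise events such as row D could be dropped.
3. In 8.1, reword the exception so that worsening of a pre-existing condition during the study counts as an AE, with causality recorded rather than used as an entry condition.

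Both sections need the edit. The cost is wording in 8.1 and 8.2, matching CRF instructions, IRB/IEC approval of the amendment under section 9.1, and possibly a few more AE and SAE forms. No new data item is needed for relatedness.
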